Figure 2 Diagram of the Multiplicity Adjustment	54

SUMMARY OF CHANGES

PRIMARY REASON(S) FOR THIS AMENDMENT:

Section Number (s)	Section Title(s)	Description of Change (s)	Rationale
4.2.3.3	Exploratory Biomarker Research	Section 4.2.3.2 Exploratory Biomarker Research was removed.	This section was removed as it is not applicable to this study. This section was inadvertently included in the initial protocol.

ADDITIONAL CHANGE(S) FOR THIS AMENDMENT:

Section Number (s)	Section Title (s)	Description of Change (s)	Rationale
4.2.3.1	Immunogenicity Endpoints	#3 and #4 were removed	They are not trial immunogenicity endpoints
7.1.1.8.2	Concomitant Vaccinations	The following sentence was added: “Combination MMRV vaccines should not be given in this study; however, MMR and Varicella vaccines are permitted if administered concomitantly in 2 separate limbs.”	Statement was inadvertently left out of previous version of the protocol.
7.1.3.2	Blood collection for Immunogenicity Assays	“pneumo-specific” was added and “to all 15 vaccine serotypes included in V114” was removed.	To ensure that all necessary serotypes will be tested
7.1.3.3	Future Biomedical Research Samples	“which would routinely be discarded after the main study is over” was removed.	Incorrect sentence in the context of V114 development.

No additional changes.

1.0 TRIAL SUMMARY

Abbreviated Title	Safety/Immunogenicity of Different Lots of V114 vs. Prevnar 13™ in Infants
Sponsor Product Identifiers	V114 Generic name not yet assigned
Trial Phase	II
Clinical Indication	Prevention of pneumococcal disease
Trial Type	Interventional
Type of control	Active control without placebo
Route of administration	Intramuscular
Trial Blinding	Double-blind
Vaccination Groups	Subjects will be randomly assigned to receive V114 Lot 1, V114 Lot 2, or Prevnar 13™ (control). See Section 5.2 for a detailed description of the V114 lots).
Number of trial subjects	Approximately 1,050 subjects will be enrolled.
Estimated duration of trial	The Sponsor estimates that the trial will require approximately 2 years from the time that written informed consent is provided for the first subject until the last subject's last study-related phone call or visit. For purposes of analysis and reporting, the overall trial ends when the Sponsor receives the last serological results.
Duration of Participation	Each subject will participate in the trial for approximately 11 to 14 months from the time the parent/legal guardian signs the informed consent form (ICF) through the final contact. Each subject will receive 4 doses of the trial vaccine given at approximately 2, 4, 6, and 12 to 15 months of age. After each vaccination, the trial subject will be observed for 30 minutes and followed for 14 days for injection site and systemic adverse events (AEs). Serious adverse events (SAEs) will be collected from the time the consent form is signed through 30 days post-dose 4 (PD4) and/or completion of the subject's participation in the trial, see Section 7.2 for details. Blood samples will be collected 1 month following dose 3, immediately prior to dose 4, and 1 month following dose 4.
Randomization Ratio	1:1:1

A list of abbreviations used in this document can be found in Section 12.4.

2.0 TRIAL DESIGN

2.1 Trial Design

This is a multicenter, randomized, double-blind trial to evaluate the safety, tolerability, and immunogenicity of 2 different lots of V114 in healthy infants to be conducted in conformance with Good Clinical Practices (GCPs). Prevnar 13™ (pneumococcal 13-valent conjugate vaccine [diphtheria CRM₁₉₇ protein], Wyeth Pharmaceuticals, Inc., Philadelphia, Pa) will serve as the active control. This trial will enroll approximately 1,050 healthy infants 6 to 12 weeks (≥ 42 to ≤ 90 days) of age. Subjects will be randomly assigned to receive V114 Lot 1 (n=350), V114 Lot 2 (n=350) or Prevnar 13™ (n=350). (See Section 5.2 for a detailed description of the V114 lots).

A 0.5mL intramuscular dose of the trial vaccine will be administered to healthy infants at approximately 2, 4, 6, and 12 to 15 months of age.

[figure not shown]
The safety and tolerability profile of V114 will be carefully monitored throughout the trial by both the SPONSOR in accordance with standard procedures and by an external Data Monitoring Committee (eDMC). (Details regarding in-house blinding of SPONSOR personnel can be found in Section 5.2.3. ‘Trial Blinding’).

Any trial subject with a serotype-specific anti-pneumococcal immunoglobulin G (IgG) value, as measured by pneumococcal electrochemiluminescence (Pn ECL) assay below 0.35 µg/mL for serotype 19A (individually) or below 0.35 µg/mL for 4 or more of the other serotypes in common with Prevnar 13™ at 1 month post-dose 3 (PD3) will be discontinued from the study and offered an additional dose of licensed pneumococcal conjugate vaccine outside of this protocol. See Section 5.6 (Rescue Medications & Supportive Care) for additional details of the rescue plan.

Specific procedures to be performed during the trial, as well as their prescribed times and associated visit windows, are outlined in the Trial Flow Chart - Section 6.0. Details of each procedure are provided in Section 7.0 – Trial Procedures.

2.2 Trial Diagram

The trial design is shown in [Figure 1](#).

†Refer to Protocol Section 6.0 Trial Flow Chart for acceptable age ranges and/or visit windows

Figure 1 Trial Design

3.0 OBJECTIVE(S) & HYPOTHESIS(ES)

3.1 Primary Objective(s) & Hypothesis(es)

In healthy infants receiving one of the 2 V114 lots or Prevnar 13™ at approximately 2, 4, 6, and 12-15 months of age:

1. **Objective:** To describe the safety and tolerability profiles of 2 different lots of V114 [Lot 1 (V114-1), Lot 2 (V114-2)], after each dose.

2. **Objective:** To demonstrate that V114 (either V114-1 or V114-2) is non-inferior to Prevnar 13TM for the 13 shared serotypes (1, 3, 4, 5, 6A, 6B, 7F, 9V, 14, 18C, 19A, 19F, and 23F), based on the proportion of subjects meeting serotype-specific immunoglobulin G (IgG) threshold value of ≥ 0.35 $\mu\text{g/mL}$ at 1 month post-dose 3 (PD3).

Hypothesis: The proportion of subjects receiving V114 (either V114-1 or V114-2) who have serotype specific IgG ≥ 0.35 $\mu\text{g/mL}$, as measured by the Pn ECL assay, for each of pneumococcal serotypes 1, 3, 4, 5, 6A, 6B, 7F, 9V, 14, 18C, 19A, 19F, and 23F at 1 month PD3 is non-inferior to that for recipients of Prevnar 13TM.

[The statistical criterion for non-inferiority corresponds to the lower bound of the adjusted 95% CI of the proportion difference (V114 minus Prevnar 13TM) being greater than -0.15 for each of the 13 shared serotypes.]

3. **Objective:** To evaluate the serotype-specific IgG geometric mean concentrations (GMCs) of V114-1, V114-2, and Prevnar 13TM, and the IgG GMC ratios between each of the two V114 lots and Prevnar 13TM for all 15 serotypes included in V114 (1, 3, 4, 5, 6A, 6B, 7F, 9V, 14, 18C, 19A, 19F, 22F, 23F, and 33F) at 1 month PD3.

3.2 Secondary Objective(s) & Hypothesis(es)

1. **Objective:** To evaluate the serotype-specific IgG GMCs of V114-1, V114-2, and Prevnar 13TM, and the IgG GMC ratios between each of the two V114 lots and Prevnar 13TM for all 15 serotypes included in V114 at pre-dose 4 and 1 month post-dose 4 (PD4).

3.3 Exploratory Objective(s)

1. To evaluate the serotype-specific IgG response rates of V114-1, V114-2, and Prevnar 13TM, and the differences in IgG response rates between each of the two V114 lots and Prevnar 13TM for the 2 serotypes unique to V114 (22F and 33F) at 1 month PD3 and all 15 serotypes included in V114 at pre-dose 4 and 1 month PD4. The serotype-specific IgG response rate will be based on the proportion of subjects achieving serotype-specific IgG ≥ 0.35 $\mu\text{g/mL}$ as measured by the Pn ECL assay.
2. To describe the proportions of subjects with opsonophagocytic killing activity (OPA) titer ≥ 8 and OPA geometric mean titers (GMTs) as measured by MOPA-4 assay in subjects receiving V114-1, V114-2, and Prevnar 13TM for all 15 serotypes included in V114 at 1 month PD3, pre-dose 4, and 1 month PD4.

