Functional antibody activity, OPA, will also be evaluated in approximately 50% of infants enrolled at US study sites with sufficient serum available at PD3 to perform both the Pn ECL assay and the OPA testing on all 15 serotypes in V114. Pre-dose 4 and PD4 OPA measurements will be conducted for all of the subjects who had PD3 OPAs performed and for which there is sufficient serum. The proportion of subjects meeting OPA titer ≥ 8 and the OPA GMTs at PD3 and separately at pre-dose 4 and PD4 will be summarized for each serotype.

Primary immunogenicity endpoints for the comparison of pneumococcal conjugate vaccines in children are based on immunoglobulin (IgG) antibodies responses. Such responses are consistent with the recommendations from the World Health Organization (WHO) and many regulatory agencies worldwide and include serotype-specific measurements of the following endpoints: a) the proportion of subjects achieving IgG antibody concentrations $\geq 0.35 \mu\text{g/mL}$ four weeks after third dose; and b) the IgG geometric mean antibody concentration (GMC) measured 4 weeks after the third and fourth doses. For new serotypes not included in licensed pneumococcal conjugate vaccine used as comparator, non-inferiority comparisons are made to the lowest response rate observed to any vaccine serotype among recipients of the licensed vaccine.

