8.4.1 Immunogenicity Endpoints

The primary immunogenicity endpoints include:

- (1) The proportion of subjects with serotype-specific IgG ≥ 0.35 $\mu\text{g/mL}$ measured by the Pn ECL assay at 1 month post-dose 3 for the 13 common serotypes (1, 3, 4, 5, 6A, 6B, 7F, 9V, 14, 18C, 19F, 19A, and 23F) between V114 and Prevnar 13TM in recipients of either lot of V114 and Prevnar 13TM.
- (2) The IgG GMCs for the 13 common serotypes (1, 3, 4, 5, 6A, 6B, 7F, 9V, 14, 18C, 19F, 19A, and 23F) between V114 and Prevnar 13TM, and 2 serotypes unique to V114 (22F and 33F) in recipients of either lot of V114 and Prevnar 13TM, based on the serotype-specific IgG responses as measured by the Pn ECL assay at 1 month post-dose 3.

The secondary and exploratory immunogenicity endpoints include:

- (1) The proportion of subjects with serotype-specific IgG ≥ 0.35 $\mu\text{g/mL}$ measured by the Pn ECL assay at 1 month post-dose 3 for the 2 serotypes unique to V114 (22F and 33F) in recipients of either lot of V114 and Prevnar 13TM.
- (2) The IgG GMCs for all 15 pneumococcal serotypes (1, 3, 4, 5, 6A, 6B, 7F, 9V, 14, 18C, 19F, 19A, 22F, 23F, and 33F) in recipients of either lot of V114 and Prevnar 13TM, based on the serotype-specific IgG responses as measured by the Pn ECL assay at pre-dose 4 and 1 month post-dose 4.
- (3) The proportion of subjects with serotype-specific IgG ≥ 0.35 $\mu\text{g/mL}$ measured by the Pn ECL assay at pre-dose 4 and 1 month post-dose 4 for the 13 common serotypes (1, 3, 4, 5, 6A, 6B, 7F, 9V, 14, 18C, 19F, 19A, and 23F) between V114 and Prevnar 13TM, and 2 serotypes unique to V114 (22F and 33F) in recipients of either lot of V114 and Prevnar 13TM.
- (4) The proportion of subjects with serotype-specific OPA titer ≥ 8 and OPA GMTs as measured by the MOPA-4 assay at 1 month post-dose 3, pre-dose 4, and 1 month post-dose 4 for all 15 serotypes (1, 3, 4, 5, 6A, 6B, 7F, 9V, 14, 18C, 19F, 19A, 22F, 23F and 33F) in recipients of either lot of V114 and Prevnar 13TM.

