8.8 Multiplicity

Non-inferiority tests will be conducted for the 13 shared serotypes between V114 and Prevnar 13TM. The overall success for each of the V114 lots requires demonstrating non-inferior to Prevnar 13TM for each of the 13 serotypes. This approach controls the overall type I error within each lot, therefore no multiplicity adjustment will be required within each lot.

The type I error for the primary immunogenicity analysis will be controlled at the one-sided significant level of 0.025 by testing V114-1 and V114-2 simultaneously using a Hochberg approach, which is summarized in [Figure 2](#).

The success of either V114-1 or V114-2 requires demonstrating non-inferior to Prevnar 13TM for each of the 13 shared serotypes (1, 3, 4, 5, 6A, 6B, 7F, 9V, 14, 18C, 19F, 19A, and 23F).

Figure 2 Diagram of the Multiplicity Adjustment

Both lots will first be tested using a 1-sided alpha of 0.025 respectively. If all tests for both lots are significant ($p\text{-value} < 0.025$) or at least one test for both lots is non-significant ($p\text{-value} \geq 0.025$), testing is complete. However, if one lot is successful at the 1-sided alpha of 0.025 and the other is not, the successful lot will be re-tested at a more stringent 1-sided alpha of 0.0125 (0.025/2). The level of the confidence interval will align with the type I error during the re-testing procedure, i.e., the 97.5% CI will be provided if only one of the two lots succeeds. Testing in this manner controls the type I error for the primary immunogenicity analysis at the 1-tailed $\alpha=0.025$.

The Haybittle-Peto rule using 1-sided significance level of $\alpha =0.0005$ will be utilized to account for the interim analysis. The final analysis will still be evaluated at a 1-sided significance level of $\alpha =0.025$ as described in Section 8.7.

No multiplicity adjustments will be made for the safety comparisons.

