8.9 Sample Size and Power Calculations

8.9.1 Immunogenicity Analyses

Approximately 1050 subjects will be enrolled, with approximately 350 subjects in each of the three vaccination groups. For the primary immunogenicity hypotheses, the power is simulated based on the Hochberg approach. There is $>90\%$ power to declare non-inferiority to Prevnar 13TM for the 13 common serotypes between V114 and Prevnar 13TM and superiority for the two serotypes unique to V114 for at least one of the V114 lots based on the proportion of subjects meeting the serotype-specific IgG ≥ 0.35 $\mu\text{g/mL}$. This power assumes an 85% evaluability rate (~ 298 subjects per group), a non-inferiority margin of -0.15 for the difference (V114 – Prevnar 13TM), and a serotype-specific true percentage of the response rate based on the group level results from the V114-003 CSR, the V114-004 interim analysis and the knowledge of the V114 formulation that will be used in this trial. Based on this knowledge, it was conservatively assumed that the true response rates of V114 will be 0.05 lower than that of Prevnar 13TM for serotypes 6A, 6B, and 19A, 0.20 higher for serotype 3, and the same for the remaining serotypes. The assumption of the true percentage for each serotype can be found in [Table 6](#).

Note that the overall power is sensitive to the assumed response rate of V114 for the serotypes which are assumed to have lower response rates (6A, 6B, and 19A). For example, if the V114 response rate for 6B is decreased from 0.82 to 0.80 (0.07 lower than that of Prevnar 13TM), the power will be $\sim 80\%$.

Further details are provided in the sSAP.

Table 6

PCI

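### For 22F and 33F the planned response-rate difference is from a vaccine that lacks both serotypes, so it says little about adequacy; the reference described in Section 4.2.3.1 is not used, and the power statement counts a superiority result that the plan never tests

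*Combined protocol and SAP*

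**What the plan says.** Section 4.1.1 lists the Prevnar 13 serotypes; 22F and 33F are not among them.

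The rationale in Section 4.2.3.1 states that, for serotypes absent from the licensed comparator, "non-inferiority comparisons are made to the lowest response rate observed to any vaccine serotype among recipients of the licensed vaccine". It gives no margin.

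The operative sections plan something else for these two serotypes:

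- **Section 3.3, objective 1:** response rates by group, and "the differences in IgG response rates between each of the two V114 lots and Prevnar 13TM for the 2 serotypes unique to V114", at 1 month post-dose 3.
- **Section 8.4.1:** the matching endpoint is the proportion at or above 0.35 µg/mL "for the 2 serotypes unique to V114 (22F and 33F) in recipients of either lot of V114 and Prevnar 13TM".
- **Section 3.1, objective 3:** the GMCs and "the IgG GMC ratios between each of the two V114 lots and Prevnar 13TM for all 15 serotypes included in V114", estimated without a hypothesis.
- **Section 8.8:** "Non-inferiority tests will be conducted for the 13 shared serotypes between V114 and Prevnar 13TM". No test on 22F or 33F appears there.
- **Sections 8.1 and 8.9.1:** the power claim of more than 90% covers non-inferiority on the shared serotypes and also "superiority for the two serotypes unique to V114 for at least one of the V114 lots".

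**The concern.** The two added serotypes are what V114 offers beyond the comparator (Sections 4.1.1 and 4.3). A same-serotype difference from recipients of a vaccine without the antigen will be positive for almost any conjugate that works at all. A clearly positive interval therefore separates some response from none. It does not separate a strong response from a weak one. The contrast that the protocol's own rationale describes would do more, and no difference, interval or criterion is planned for it.

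There is also a mismatch inside the plan. The power statement treats superiority on 22F and 33F as part of success, but Section 3 has no such hypothesis, Section 8.6 no such test, and Section 8.8 defines success on the 13 shared serotypes only. At stake are how informative the between-group result for the added serotypes is, and whether the stated power describes the hypothesis actually tested.

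**Working it through.** **Inputs from the documents.** 350 per group and 85% evaluability (8.9.1); one-sided 0.025 with Hochberg over the two lots (8.8); margin -0.15, set for the 13 shared serotypes (3.1, 8.6.1); 6B rates of 0.82 or 0.80 for V114 against 0.87 for Prevnar 13 (8.9.1); V114 assumed 0.05 lower on 6A, 6B and 19A and 0.20 higher on serotype 3 (8.9.1).

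**Assumed, because Table 6 is redacted.** Prevnar 13 rates for 22F and 33F: 0.05 to 0.30. Lowest Prevnar 13 shared-serotype rate: 0.60 to 0.80. The upper end follows from the plan: V114 on serotype 3 cannot exceed 1.00, so Prevnar 13 on serotype 3 is taken to be at most 1.00 - 0.20 = 0.80. The plan states no level for superiority on 22F and 33F; one-sided 0.025 is used.

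**Step 1: the plan's own figures.** 350 × 0.85 = 297.5, which matches the stated 298. Power for at least one lot was simulated for the 13 shared serotypes only. It used the Miettinen-Nurminen test, Hochberg, a shared control arm and independent serotypes. Assumed Prevnar 13 rates were 0.90 to 0.92 for 6A, 0.95 for 19A, 0.70 for serotype 3, and 0.90 or 0.95 for the rest. Power was 93.5 to 95.0% with V114 6B at 0.82, and 79.5 to 81.0% at 0.80. This agrees with the stated figures of above 90% and about 80%, with 22F and 33F left out. Varying the assumed 6A and 19A rates from 0.87 to 0.97 gives 85 to 96% and 71 to 83%.

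**Step 2: V114 rate needed for 90% power.** With the unpooled normal approximation, SE = √{[p_T(1-p_T) + p_C(1-p_C)]/298}, and 90% power requires p_T - p_C - δ = (1.960 + 1.282) × SE. Here δ = 0 for superiority and δ = -0.15 for non-inferiority.

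| Comparison | Assumed Prevnar 13 rate | V114 rate needed |
|---|---|---|
| Same-serotype superiority | 0.05 | 0.124 |
| | 0.10 | 0.193 |
| | 0.20 | 0.315 |
| | 0.30 | 0.427 |
| Non-inferiority to lowest shared serotype | 0.60 | 0.581 |
| | 0.70 | 0.673 |
| | 0.80 | 0.760 |

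First row: SE = √[(0.1088 + 0.0475)/298] = 0.0229, and 0.05 + 3.242 × 0.0229 = 0.124. Last row: SE = √[(0.1824 + 0.1600)/298] = 0.0339, and 0.80 - 0.15 + 3.242 × 0.0339 = 0.760.

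**Step 3: check with the planned method.** By the Miettinen-Nurminen score test, the lowest observed V114 rate that passes superiority is 9.4% when Prevnar 13 shows 5%, and 37.6% when it shows 30%. The lowest that passes non-inferiority to the lowest shared serotype is 53.0% when that serotype shows 60%, and 71.8% when it shows 80%.

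**Step 4: does superiority affect the stated power?** At a true V114 rate of 0.40 and a Prevnar 13 background of 0.05 to 0.20, superiority power exceeds 99.9%. Including or dropping it barely moves the claim of more than 90%.

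**Step 5: ranking of the lots.** Both lots are compared with the same Prevnar 13 arm. For any reference rate R, (L1 - R) - (L2 - R) = L1 - L2, so the choice of reference cannot change the order of the lots on 22F or 33F.

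**The case against.** The strongest reply is that the information is already there. Section 3.3 reports the 22F and 33F response rates by group, Section 8.6.1 adds within-group GMCs with 95% CIs, and OPA results for all 15 serotypes are described in a subset. The Prevnar 13 rates for the shared serotypes come from the primary endpoint. A weak rate would be visible beside them. This stands: a reader might infer that the trial cannot show whether the added serotypes respond adequately, and the documents do not support that. What is missing is a planned difference with an interval.

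Three other strong readings also fail.

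- **That the plan breaks a commitment in Section 4.2.3.1.** The sentence there describes general practice, sets no margin, and does not bind this trial. The trial-specific endpoints listed in the same section agree with Sections 3.3 and 8.4.1.
- **That a poor lot would be declared successful on 22F or 33F.** No superiority test or success rule for these serotypes exists in Sections 3, 8.6 or 8.8, so nothing would be declared.
- **That the wrong lot could be chosen.** Step 5 rules this out as a consequence of the reference used.

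It is also fair to say that the proposed reference does not itself establish adequacy. If the lowest Prevnar 13 rate is 60%, an observed 53% passes. It compares across serotypes and borrows a margin. It is more informative than the same-serotype contrast, but it is not a proof. The supplemental SAP, to which Section 8.9.1 defers, was not available and may say more.

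**Conclusion.** The point holds as an inexpensive improvement to an exploratory comparison, together with a correction of the power wording. The planned same-serotype difference is a weak yardstick: it has 90% power at a V114 rate of about 0.12 to 0.43, against about 0.58 to 0.76 for the reference that the rationale describes. Those ranges rest on assumed Prevnar 13 rates and on a margin that the plan sets only for shared serotypes. The gap between the two yardsticks persists across the assumed ranges; its exact size does not carry over to other rates.

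The mismatch over superiority needs no assumption, since it follows from reading Sections 8.1 and 8.9.1 against Sections 3, 8.6 and 8.8. Its numerical effect is negligible. The primary hypothesis, the sample size, the type I error control and the ranking of the lots are not affected.

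**What to change.** 1. In Sections 3.3 and 8.4.1 and in Table 3, add as exploratory, for 22F and 33F at 1 month post-dose 3: each lot's response rate minus the Prevnar 13 arm's rate for its lowest-responding shared serotype, with a Miettinen-Nurminen 95% CI. Read it against -0.15, and say that this value is borrowed from the shared-serotype hypothesis as a reference.
2. Name the reference serotype beforehand from Table 6. Picking the lowest from the observed data would bias the reference rate slightly downward.
3. Keep the same-serotype difference, labelled as descriptive.
4. In Sections 8.1 and 8.9.1, remove superiority for the two unique serotypes and state power for the 13-serotype hypothesis only. The figure above 90% should barely change.

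The cost is four extra intervals (two serotypes, two lots) from data already collected, plus wording. Power is not an obstacle: at a true V114 rate of 0.80, the added comparison meets -0.15 with at least 99.5% probability against lowest rates of 0.60 to 0.80. The downsides are the cross-serotype reference and the borrowed margin, and both should be stated where the result is reported.
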